## 8.3 Reporting

### 8.3.1 Reporting of SAE

All SAEs (initial and FU information) will be reported electronically through the Electronic Data Capture (EDC) platform within 24 hours of the discovery of the event. Manual SAE report forms are available in the Trial Reference Manual, however manual SAE report forms should be forwarded only in the event that electronic capturing is not functioning and must be entered on the AE eCRF when it again becomes available. BN or designee may request FU and other additional information from the Investigator (e.g., hospital admission/discharge notes, laboratory results, etc.).

*The investigator should not delay reporting because of missing information. Nonetheless, the report should be as complete as possible.* This initial notification should include, at a minimum, sufficient information to permit identification of the following:

- The reporter (investigator's name and contact information)
- The subject
- Involved trial product
- AE(s)
- Seriousness criterion and/or criterion for AESI
- Date of onset
- Investigator assessment of causality

The collection of SAE/AESI begins at the time the subject signs informed consent and continues for 30 days following administration of the last dose of trial product for unrelated SAEs/AESIs, and 100 days for related SAEs/AESIs after the last dose of trial product, due to the possibility of a delayed immune effect of anti-PD-1/L1 agent (atezolizumab).

All SAEs, irrespective of the treatment received by the subject, must be reported to BN's PV department within 24 hours of the investigator learning of the event.

All deaths should be reported with the primary cause of death as the SAE term, as death is typically the outcome of the event, not the event itself. The primary cause of death on the autopsy report should be the term reported. Autopsy and postmortem reports must be forwarded to BN's PV department as outlined above.

If trial product is discontinued because of an SAE, this information must be included in the SAE report.

Investigators must report SAEs to their governing IRBs in writing as soon as possible and in accordance with national and local laws and regulations.

### **8.3.2 Reporting of AESIs**

As noted in [Section 8.1.3](#), IMAEs and cardiac events are considered AESIs as well as the AESI requirements from the manufacturer of Tecentriq®. AESIs occurring throughout the reporting period are to be recorded on the AE eCRF by marking the appropriate tick box as well as the (S)AE/AESI eCRF, regardless of seriousness or attribution. AESIs have to be reported immediately after detection. An automatic email notification will be sent to the relevant project members as soon as an AESI has been reported in the EDC. In addition to the above mentioned eCRFs, an IMAE eCRF is also linked to the (S)AE / AESI eCRF in the EDC and must be completed by the investigator when reporting an IMAE AESI.

Appendix , [Section 17.3](#) outlines the reporting process and timelines for AESIs.

### **8.3.3 Reporting of Pregnancies**

Trial product exposed pregnancies cannot be excluded with certainty. Subjects who are discovered to be pregnant prior to the first vaccination will be excluded from the trial and regarded as screen failures. Subjects who are discovered to be pregnant during the active trial period must not receive additional doses of CV301 or atezolizumab, but may continue other trial procedures at the discretion of the investigator. All reports where the embryo or fetus may have been exposed to the trial product (either through maternal exposure or transmission of trial product via semen following paternal exposure) should be followed-up until delivery in order to collect information on the outcome of the pregnancy.

Subjects should be instructed to notify the investigator if it is determined – also after completion of the trial – that they became pregnant either during the trial or within 30 days after receiving the last dose of CV301 dose or 5 months after the last dose of atezolizumab.

If a subject becomes pregnant during the active trial period this must be reported to BN on a manual Pregnancy Notification Report Form (available in the Site Reference Manual) within 24 hours of the investigator's becoming aware of the event.

Female subjects or female partners of male subjects will be counseled as to any possible known risks to either the partner or the child. At the current time, no pregnancies have been reported for subjects treated with CV301 and therefore no data exist that would identify risks to partner or child. It is the responsibility of the investigator to counsel the subject on the identified risks of atezolizumab according to the USPI as well as disclose any known risks prior to the subject consenting to receive treatment with atezolizumab.

A pregnancy should be followed till outcome, and the health status of the mother and child including date of delivery and the child's gender and weight should be reported to BN as soon as

possible after delivery on a Pregnancy Outcome Report Form (available in the Site Reference Manual). The female partner should sign the Pregnant Partner Informed Consent Form for follow up.

Any event during pregnancy fulfilling the criteria for an SAE will be reported as SAE to BN PV department. However, hospitalization for delivery is a prospectively planned hospitalization and is not considered a SAE per se. Pregnancies resulting in an abnormal outcome (i.e., congenital abnormality, birth defect, or infant death) should be reported as SAEs within 24 hours of the investigator becoming aware of the event.

## 9 Statistical Considerations

This is a single-arm, multi-center, two-cohort Phase 2 clinical trial to assess the safety and preliminary efficacy of CV301 in combination with PD-1/L1 blockade in subjects with locally advanced or metastatic urothelial cancer including the bladder, ureter, or renal pelvis. The trial will be performed as a two-stage design ([Simon, 1989](#)) within the following two cohorts:

Cohort 1: Ineligible for cisplatin-containing chemotherapy

Cohort 2: Previously treated with standard first-line cisplatin-based chemotherapy, PD-1/L1 naïve

The goal is to demonstrate that CV301 plus atezolizumab can induce objective responses in subjects with locally advanced or metastatic urothelial cancer in at least one of the two cohorts.

Presentation of results will occur by cohort for efficacy and exploratory endpoints, and by cohort and overall for safety, disposition, demographic, and baseline characteristic endpoints. In general, continuous endpoints will be analyzed using mean, standard deviation, median, minimum, and maximums. Categorical endpoints will be analyzed using frequencies and percentages.

### 9.1 Endpoints

See Protocol Synopsis ([Section 1.4](#)).

### 9.2 Sample Size Calculation

Refer to Protocol Synopsis ([Section 1.4](#)).

### 9.3 Analysis Populations

For the purpose of statistical analysis, there will be 2 analysis populations: Full Analysis Set (FAS) and the Efficacy Evaluable Set (EE).

The FAS consists of all subjects taking any amount of trial vaccine, whether MVA-BN-CV301 or FPV-CV301. The FAS will be the primary population for all analyses.

The EE Set consists of all subjects from the FAS who received 2 prime doses of MVA-BN-CV301 (Weeks 1 and 4).

The EE population will be used in sensitivity analyses for efficacy.

Subjects who failed to meet the EE Set criteria will be replaced unless 4 or more responses in Cohort 1 (or 3 or more responses in Cohort 2) have been observed for the FAS population, or the number of responders will still be less than 4 in Cohort 1 (or 3 in Cohort 2) even if all replacement subjects would be responders. If there are more than 14 evaluable subjects in Cohort 1 (or 13 in Cohort 2) at the end of Stage 1 analysis, or more than 33 in Cohort 1 (or 35 in Cohort 2) evaluable subjects at the end of Stage 2 analysis, primary evaluation will be based on the first 14 (or 13) accrued or first 33 (or 35) accrued FAS subjects.

## **9.4 Subject Disposition**

The number and percent of subjects who meet all protocol inclusion and exclusion eligibility criteria, who discontinue trial product, and reason for trial product discontinuation will be presented using the FAS. Subject participation by site will also be presented.

## **9.5 Subject Characteristics**

Subject characteristics including demographics, disease characteristics, prior cancer therapies, and relevant medical history will be summarized for the purpose of describing the subject population using the FAS.

## **9.6 Prior/Concomitant Medications**

All concomitant medications (including Long Term FU anti-cancer treatments) and prior medications will be coded to Anatomic-Therapeutic-Chemical (ATC) drug classes and preferred drug names using the WHO Drug Dictionary. The incidence of prior and concomitant medication usage will be summarized by ATC class and preferred drug names for the FAS.

## **9.7 Efficacy Analysis**

### **9.7.1 Primary Efficacy Analysis**

The ORR is defined as the proportion of subjects with an objective tumor response (CR or PR) based on RECIST 1.1 evaluations as performed by the investigator. Based on prior published results with atezolizumab, the null ORR for Cohort 1 is 0.23, and for Cohort 2 is 0.15.

Cohort 1: In the first stage, 14 subjects will be accrued. If there are 3 or fewer responses in these 14 subjects, the cohort will be stopped. Otherwise, 19 additional subjects will be accrued for a total of 33. The null hypothesis will be rejected if 13 or more responses are observed in 33 subjects. This design yields an actual type I error rate of 0.0244 and power of 0.7027 when the true ORR is 0.43 for the combination.

Cohort 2: In the first stage, 13 subjects will be accrued. If there are 2 or fewer responses in these 13 subjects, the cohort will be stopped. Otherwise, 22 additional subjects will be accrued for a total of 35. The null hypothesis will be rejected if 10 or more responses are observed in 35 subjects. This design yields an actual type I error rate of 0.0249 and power of 0.7092 when the true ORR is 0.33 for the combination.

In the case that the number of responses required to move to Stage 2, individually per cohort, is met in the FAS population, the study will move to Stage 2 without enrolling the full EE Set. If Stage 1 results are not clear after enrolling the prescribed number of Stage 1 subjects in the FAS, enrollment will continue until the EE Set meets the prescribed number of Stage 1 subjects for the interim futility analysis. In the event continuing enrollment of the EE Set would still not produce a positive outcome for Stage 1, the cohort will be discontinued without meeting the full Stage 1 sample size for the EE set.

For the final primary efficacy analysis, the number and percent of subjects with OR, and in each category of objective tumor response, will be summarized based on the FAS. The two-sided 90% exact binomial confidence interval for the ORR will be calculated using the Clopper-Pearson method.

Sensitivity analyses will be performed based on a repeated analysis using the EE Set, as well as any potential immune-related responses observed. In case these immune-related responses are observed, ORR analyses using iRECIST criteria will also be provided. For iRECIST, complete or partial responses are still able to be achieved after an initial unconfirmed progression, whereas with RECIST 1.1 once any evidence of progression is recorded, no further responses are able to be evaluated. For subjects who are not evaluated by iRECIST criteria, their tumor response based on RECIST 1.1 response guidelines will be used.

## **9.7.2 Secondary Efficacy Analyses**

### **9.7.2.1 Progression-Free Survival**

PFS is defined as the time interval from first treatment to objective tumor progression or death. Accordingly, the precise definition of progression and the timing of CT scans to document progression are very important. Every effort must be made to assure that timeframes for FU CT scans are achieved. Assessments must be adequate to evaluate target lesions, non-target lesions, and to search for new lesions.

The secondary endpoint of PFS will be based on the investigator's assessment using RECIST 1.1 response guidelines. PFS will be defined as the time from the day of first treatment with trial product to the start of disease progression or death (any cause), whichever occurs first. Subjects who do not have disease progression or have not died will be censored at the date when the last tumor assessment determines a lack of progression. If a subject begins a new anti-cancer therapy or has radiotherapy or surgery at a lesion site prior to documented progression (or death), the subject will be censored at the last assessment where the subject was documented as progression free prior to the intervention.

The Kaplan-Meier curve for PFS and the median PFS will be presented for the FAS Set.

Additionally, an investigator assessed PFS analysis that includes both investigator-judged PD according to RECIST 1.1 and symptomatic deterioration will be provided.

A binary endpoint for PFS will also be analyzed at milestone time points. The number and percentage of subjects who are progression free based on the above definition at 6, 9, 12, 18, and 24 months will be summarized within the FAS. The two-sided 90% exact binomial confidence interval for the PFS at each time point will be calculated using the Clopper-Pearson method.

A recently published meta-analysis concluded that in checkpoint inhibitor trials 6-month PFS rate is recommended as an endpoint because it is the best predictor of 12-month OS rate ([Ritchie et al., 2018](#)). In the absence of prospective validation, the decision adopted is to retain 6-month PFS rate as a secondary endpoint with the aim of complement the primary endpoint ORR in the interpretation of trial results as a whole.

In case some additional immune-related responders are observed, PFS analysis using iRECIST criteria will be performed. The iRECIST modification requires a confirmation of PD at least 4 weeks later with imaging; once confirmed, the date of progression is defined as the first date that the total tumor burden was shown to have increased by at least 20% compared with the nadir. For subjects who are not evaluated by iRECIST criteria, their disease progression based on RECIST 1.1 response guidelines will be used.

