Exploratory objectives	Analysis of biopsy tissue for differences between pre- and post-treatment samples correlation to patient survival e.g.: 

• T cell receptor (TCR) clonality

• Tumor-Infiltrating-Lymphocytes (TILs)

• Protein expression for e.g. Programmed Death Ligand 1 (PD-L1) and other biomarkers

• Gene expression profiling for molecular subtyping

 Analysis of tumor DNA for Tumor mutational burden; DNA damage response gene mutations, MSI status, MMR deficiency status  Analysis of peripheral blood mononuclear cells (PBMCs) / serum for differences between pre- and post-treatment samples correlation to patient survival e.g.: 

• Antigen-specific immune responses to carcinoembryonic antigen (CEA) and mucin-1 (MUC-1) as well as to other tumor-associated antigens (TAAs) to assess antigen cascade

• Immunophenotyping of immune cell subsets by flow cytometry

• Soluble biomarkers (e.g. cytokines and classical tumor markers)

• TCR clonality

• PD-1/L1 staining

Primary endpoint	Proportion of subjects with a confirmed OR (CR+PR) as per investigator assessment according to RECIST 1.1.

---

Secondary endpoints	
Safety of the combined treatment as measured by:
 

• Adverse Events (incidence, severity, and seriousness of treatment emergent adverse events [TEAEs])

• Laboratory Measures (summaries and shifts from baseline)

• Vital Signs (summaries)

 
OS defined as the time from start of treatment to the time of death from any cause.
 
Duration of response defined as the time from the initial occurrence of documented complete response (CR) or partial response (PR) (whichever occurred first) until documented disease progression or death due to any cause on trial, whichever occurred first.
 
PFS defined as the time from start of treatment to the first event of death or progressive disease (PD) per RECIST 1.1.
 
Percentage of participants with OS and PFS at 6 (PFS only), 9 (PFS only), 12, 18 and 24 months.
 
Immune-related Response Criteria assessment of response rate per iRECIST, delayed responses (pseudo-progressions), duration of response and PFS.

Trial design	Phase 2, Multicenter, Single-Arm, 2 Cohorts, Two-stage

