### **9.7.2.3 Duration of Response**

Duration of response is defined as the time from response (CR or PR, whichever occurs first) to investigator assessed progression using RECIST 1.1 or death, and will be summarized based on

the number of subjects with response in the FAS. Subjects who do not have disease progression or have not died will be censored at the date when the last radiographic tumor assessment determines a lack of progression.

Duration of response will be summarized using the product-limit estimate of median survival along with its 90% confidence interval. The Kaplan-Meier curve will summarize duration of response graphically.

In case some additional immune-related responders are observed, duration of response analyses using iRECIST criteria will be provided. For subjects who are not evaluated by iRECIST criteria, their tumor response based on RECIST 1.1 response guidelines will be used.

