In case some additional immune-related responders are observed, PFS analysis using iRECIST criteria will be performed. The iRECIST modification requires a confirmation of PD at least 4 weeks later with imaging; once confirmed, the date of progression is defined as the first date that the total tumor burden was shown to have increased by at least 20% compared with the nadir. For subjects who are not evaluated by iRECIST criteria, their disease progression based on RECIST v1.1 response guidelines will be used.

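### iRECIST endpoints are listed without condition but analyzed only if immune-related responders appear, and the only iRECIST progression date is a 20% burden rise

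*Protocol*

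**What the plan says.** **Endpoint lists.** The secondary endpoints in Protocol 1.4 include "Immune-related Response Criteria assessment of response rate per iRECIST, delayed responses (pseudo-progressions), duration of response and PFS". SAP 2.6.2 carries the same item. Neither attaches a condition.

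**Analysis text.** Each iRECIST analysis has a trigger:

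- Response rate: Protocol 9.7.1 says "In case these immune-related responses are observed, ORR analyses using iRECIST criteria will also be provided". SAP 4.4.5.1 offers it for immune-related response cases.
- PFS: Protocol 9.7.2.1 sets the condition "In case some additional immune-related responders are observed", and SAP 4.4.5.2.1 matches it: "In case some additional immune-related responders are observed, PFS analysis using iRECIST criteria will be performed".
- Duration of response: Protocol 9.7.2.3 says "In case some additional immune-related responders are observed, duration of response analyses using iRECIST criteria will be provided", matching SAP 4.4.5.2.3.

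**Date rule.** Protocol 9.7.2.1 and SAP 4.4.5.2.1 require iRECIST progression to be confirmed by imaging at least 4 weeks later. Once it is, "the date of progression is defined as the first date that the total tumor burden was shown to have increased by at least 20" per cent from nadir. Neither document gives another iRECIST date or defines total tumor burden.

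**Fallback.** Protocol 9.7.2.1 adds: "For subjects who are not evaluated by iRECIST criteria, their disease progression based on RECIST 1.1 response guidelines will be used".

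**Other routes to progression.** The same section wants scans adequate "to evaluate target lesions, non-target lesions, and to search for new lesions". The response table in Protocol 17.4 makes non-target progression, or any new lesion, overall progressive disease.

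**The concern.** There are two faults, both in how the iRECIST endpoint is carried into analysis.

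First, whether a pre-specified secondary endpoint is analyzed depends on its own result. SAP section 1 undertakes to follow the plan completely and to label unforeseen analyses as unplanned. If the trigger is not met, the listed endpoint has no planned analysis, although SAP 4.5 declares no departure from the protocol's analyses. The trigger is also loosely drawn: how many responders count as some is not stated, nor whether the test is per cohort or for the whole trial.

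Second, the date rule covers one route to progression, while the trial's own criteria recognize three. A confirmed progression without a 20% burden rise has no iRECIST date when it occurs, so the rule as written places the event too late or censors the subject. In an open-label, single-arm trial with investigator-assessed response, complete pre-specification is the main protection for these supplementary results.

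**Working it through.** **Step 1. Follow each type of subject through the written rules.** Protocol 4.2.5.1 lets the investigator continue treatment past RECIST 1.1 progression when pseudoprogression is suspected, with re-evaluation under iRECIST.

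| Course after RECIST 1.1 progression | Adds a responder? | Result under the iRECIST text |
|---|---|---|
| (a) Not confirmed, later CR or PR | Yes | Trigger met; ORR and PFS change |
| (b) Not confirmed, then stable disease | No | iRECIST PFS is longer than RECIST 1.1 PFS, but the trigger is not met |
| (c) Confirmed, burden up at least 20% | No | Date available |
| (d) Confirmed through non-target or new lesions, no 20% rise | No | No date then; later growth, death or censoring decides |
| (e) Treatment stopped, not evaluated by iRECIST | No | RECIST 1.1 date, through the fallback |

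Case (b) shows that the trigger does not match the PFS endpoint. Case (d) is the gap in the date rule.

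**Step 2. Direction of the error in case (d).** Death is a PFS event, so these subjects are not lost as a class. Their event moves to the first later 20% rise or to death. If neither is observed, the subject is censored. If the RECIST 1.1 censoring rule for new anti-cancer therapy is carried over, starting such therapy also censors the subject at the last progression-free scan. Each path lengthens iRECIST PFS. Duration of response is affected in the same way if it uses the same date; Protocol 9.7.2.3 and SAP 4.4.5.2.3 supply no other iRECIST date.

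**Step 3. How often might the trigger fail?** This is illustrative only.

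Inputs from Protocol 2.1: 5 subsequent responses among 137 patients treated past progression, and 310 patients in Cohort 2 of the cited atezolizumab study. Cohort sizes come from Protocol 9.7.1. Check of the stated figure: 5/137 = 0.0365, given as 3.6%.

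Assumed rate q of added responders per enrolled subject: from 5/310 = 0.0161 (taking all 310 as the denominator) to 5/137 = 0.0365 (as if every subject continued past progression). Taking one added responder in a cohort as enough, P(trigger not met) = (1 − q)^n:

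| Cohort and stage | n | q = 0.0161 | q = 0.0365 |
|---|---|---|---|
| Cohort 1, full | 33 | 0.585 | 0.293 |
| Cohort 2, full | 35 | 0.566 | 0.272 |
| Cohort 1, stopped at Stage 1 | 14 | 0.796 | 0.594 |
| Cohort 2, stopped at Stage 1 | 13 | 0.809 | 0.617 |

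If these rates carry over to the combination, an unmet trigger is an ordinary outcome.

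**Step 4. Can the bias in PFS be sized?** No. It needs the share of subjects evaluated by iRECIST, the share of their confirmed progressions that occur without a 20% rise, and the delay to later growth or death. The documents give none of these for this trial.

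**The case against.** Several points on the other side are sound.

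- **The conditional tables would mostly be redundant.** As both documents describe it, iRECIST allows responses after an unconfirmed progression and requires progression to be confirmed. Relative to RECIST 1.1 it can add responders and remove or delay progressions. With no added responder, the two response rates are equal, and the iRECIST PFS left unrun would be no worse than the RECIST 1.1 PFS that is always reported. A reader might infer that the trigger hides unfavorable results; the documents do not support that. What stands is that a listed endpoint may go unanalyzed and that case (b) is missed.
- **The fallback narrows the date gap.** Subjects not evaluated by iRECIST keep their RECIST 1.1 date. Since Protocol 4.2.5.1 ties iRECIST re-evaluation to continued treatment, the gap mainly concerns subjects treated past progression. It does not help those who are evaluated.
- **Total tumor burden may include new lesions.** If the undefined term covers measurable new lesions, part of the gap closes. Non-target progression and non-measurable new lesions remain undated.
- **The protocol cites iRECIST guidance.** It does so for re-evaluation, without saying that the guidance replaces the 20% sentence in the analysis sections.
- **The analyses are supplementary.** The iRECIST ORR is called a sensitivity analysis, and no iRECIST result enters the hypothesis test.

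**Conclusion.** The point holds in both parts. The analysis sections make an unconditional secondary endpoint depend on the result, and the iRECIST date rule leaves out progression routes that the protocol itself recognizes. For subjects evaluated by iRECIST, the second fault biases iRECIST PFS upward, and duration too if the same date is used. The size is unknown.

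A reader might put a figure on it by removing 20%, 30% or 40% of the hazard from a 6-month PFS of 35%: 0.35^0.8 = 43%, 0.35^0.7 = 48%, 0.35^0.6 = 53%. The documents do not support those figures. The 35% starting value is in neither document. The formula deletes a share of all events, deaths included, and assumes the affected subjects never have a later event. It also treats every progressor as evaluated by iRECIST. Nor would it describe a planned milestone: the PFS rates from 6 to 24 months in Protocol 9.7.2.1 and SAP 4.4.5.2.1 rest on the RECIST 1.1 definition.

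The primary ORR test with its error rate and power, RECIST 1.1 PFS, RECIST 1.1 duration and the milestone PFS rates are unaffected. The trigger probabilities rest on an assumed per-subject rate borrowed from atezolizumab alone and show only that non-reporting is realistic.

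**What to change.** 1. Remove the condition everywhere it occurs: Protocol 9.7.1, 9.7.2.1 and 9.7.2.3, and SAP 4.4.5.1, 4.4.5.2.1 and 4.4.5.2.3. The response-rate trigger is worded differently from the other two, so deleting one phrase is not enough. State that iRECIST ORR, PFS and duration of response are always reported, by cohort.
2. In Protocol 9.7.2.1 and SAP 4.4.5.2.1, replace the 20% sentence with: *the date of the first unconfirmed progression by any route (target, non-target or new lesion) that is later confirmed*. Refer to the same definition in the duration-of-response sections.
3. Keep the RECIST 1.1 fallback for subjects not evaluated by iRECIST.

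The cost is a wording change and a few routine tables. It needs no new data, scans or subjects.
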